3.3 Exclusion Criteria

- Patients with blastoid histology
- Patients with known or suspected CNS involvement
- Viral infection with HIV or hepatitis type B or C. Seropositive HBV patients are eligible if they are negative for HBV DNA by PCR and receive concomitant antiviral therapy during treatment and for additional six months after coming off study.
- Prior history of malignancies other than MCL unless the patient has been disease free for ≥ 5 years from the signing of the ICF. Exceptions include basal cell carcinoma or squamous cell carcinoma of the skin; carcinoma in situ of cervix; carcinoma in situ of breast, or localized prostate cancer
- Active uncontrolled systemic fungal, bacterial or viral infection (defined as ongoing signs/symptoms related to the infection without improvement despite appropriate antibiotics, antiviral therapy and/or other treatment)
- Clinically significant cardiovascular disease such as uncontrolled or symptomatic arrhythmias, congestive heart failure, or myocardial infarction within 6 months of screening, or any Class 3 or 4 cardiac disease as defined by the New York Heart Association Functional Classification.
- Malabsorption syndrome, disease significantly affecting gastrointestinal function, or resection of the stomach or small bowel that is likely to affect absorption, symptomatic inflammatory bowel disease, partial or complete bowel obstruction, or gastric restrictions and bariatric surgery, such as gastric bypass.
- Active bleeding or history of bleeding diathesis (e.g., hemophilia or von Willebrand disease).
- Uncontrolled AIHA (autoimmune hemolytic anemia) or ITP (idiopathic thrombocytopenic purpura).
- Requires treatment with a strong cytochrome P450 3A4 (CYP3A4) inhibitor/inducer. Patients on moderate CYP3A inhibitors can be considered for study after a washout period of at least 7 days.
- Requires or receiving anticoagulation with warfarin or equivalent vitamin K antagonists (e.g., phenprocoumon) within 7 days of first dose of study drug.
- Prothrombin time (PT)/INR or aPTT (in the absence of lupus anticoagulant) $>2x$ ULN.
- Requires treatment with proton pump inhibitors (e.g., omeprazole, esomeprazole, lansoprazole, dexlansoprazole, rabeprazole, or pantoprazole). Subjects receiving proton pump inhibitors who switch to H2-receptor antagonists or antacids are eligible for enrollment to this study.

- History of significant cerebrovascular disease/event, including stroke or intracranial hemorrhage, within 6 months before the first dose of study drug.
- Major surgical procedure within 28 days of first dose of study drug. Note: If a subject had major surgery, they must have recovered adequately from any toxicity and/or complications from the intervention before the first dose of study drug.
- Patients with a history of toxic epidermal necrolysis or Stevens-Johnson syndrome
- Patients that are pregnant or breast feeding
- Known hypersensitivity to any study drug or excipients
- Patient on corticosteroids within two weeks prior to study entry, except for prednisone \leq 20 mg/day or equivalent for purposes other than treating MCL
- Use of any other experimental drug or therapy within 28 days of baseline
- Patient at high risk for deep vein thrombosis not willing to take DVT prophylaxis
- Any significant medical condition, laboratory abnormality, or psychiatric illness that would prevent the subject from participating in the study
- Known prior exposure to BTK inhibitor

4. REGISTRATION PROCEDURES

Patients will be centrally registered with the Weill Cornell Medicine (WCM), Division of Hematology and Medical Oncology, Joint Clinical Trials Office. To register a patient, email the following documents to your assigned registration contact:

- WCM Patient registration form
- First and last page of the fully executed informed consent form, plus additional pages if checkboxes for correlative studies are required.
- Fully executed HIPAA research authorization form (if separate from the consent document)
- Eligibility checklist signed and dated by investigator and research nurse
- Documentation of any eligibility waivers granted
- Redacted source documentation to verify eligibility

Central registration documents should be scanned/mailed Monday to Friday from 9:00 AM to 4:00 PM EST to study investigators and [contact], along with all other assigned registration contacts for this study. Central registration information is reviewed and entered into the REDCap database by the Coordinating Center. Patients will be assigned a sequence number for the protocol. The registering institution will then be emailed a copy of the sequence number as confirmation of a completed registration. Subjects should NOT receive any study medication prior to receipt of registration confirmation. Note that attachments larger than 4.5 MB are not accepted, so larger attachments should be split into more than one email.

Registration of patients cannot occur until the Coordinating Center has received proper documentation from the registering institution of IRB approval, including a copy of the current approval letter, stamped consent and signed FDA Form 1572, along with other required regulatory documents. These documents will be requested at site activation and may be scanned/mailed to the Coordinating Center.

5. STUDY PROCEDURES

5.1 Study Design

This is a phase 2 study to evaluate the preliminary evidence of efficacy and safety of the combination of acalabrutinib, lenalidomide and rituximab (ALR), as well as the feasibility of acalabrutinib, lenalidomide and obinutuzumab (ALO), in previously untreated mantle cell lymphoma.

The study includes an induction phase consisting of 12 cycles of ALR or ALO. Responding subjects will be eligible to enter a maintenance phase. Subjects will continue maintenance ALR or ALO until disease progression, development of unacceptable toxicity, or voluntary withdrawal. Subjects in CR wishing to attempt stem cell collection following at least 6 months of induction treatment can hold lenalidomide for up to 30 days, and restart following stem cell collection.

Subjects will be monitored for MRD status in PB at baseline, and completion of 6 and 12 cycles of induction treatment using Adaptive Biotechnology Clonoseq assay, and then every 4 cycles. Acalabrutinib and lenalidomide can be discontinued after 24 cycles of treatment (12 cycles of induction and 12 cycles of maintenance) for subjects achieving MRD-negative CR for at least 4 months during maintenance phase, while rituximab or Obinutuzumab maintenance continues. Subjects can be retreated with adding back acalabrutinib and lenalidomide at time of disease progression.

5.1.1 Induction

Cohort A: ALR cohort

- Cycles 1-12, 1 cycle = 28 days
- Acalabrutinib 100 mg BID continuous
- Lenalidomide on days 1-21 (15 mg for cycle 1, then escalate as tolerated to 20 mg)
- Rituximab 375 mg/m² on days 1, 8, 15, 21 of cycle 1 then day 1 of cycle 4, 6, 8, 10, 12

Cohort B: ALO feasibility cohort

- Cycles 1-12, 1 cycle = 28 days
- Acalabrutinib 100 mg BID continuous
- Lenalidomide on days 1-21 (15 mg for cycle 1, then escalate as tolerated to 20 mg)
- Obinutuzumab on days 1, 8, 15 of cycle 1, day 1 of cycles 2-6, then every 2 cycles

5.1.2 Maintenance

Cohort A: ALR cohort

- Ongoing, 1 cycle = 28 days
- Acalabrutinib 100 mg BID continuous
- Lenalidomide 15 mg on days 1-21
- Rituximab on day 1 of all even numbered cycles; e.g., 14, 16, 18, etc.

Cohort B: ALO feasibility cohort

- Ongoing, 1 cycle = 28 days
- Acalabrutinib 100 mg BID continuous
- Lenalidomide 15 mg on days 1-21
- Obinutuzumab on day 1 of all even numbered cycles; e.g., 14, 16, 18, etc.

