5.3.2 Lenalidomide Administration

The lenalidomide starting dose will be based on baseline calculated creatinine clearance as follows:

Table 3. Lenalidomide Starting Dose Based on Renal Function at Study Entry

Baseline Calculated Creatinine Clearance (by Cockcroft-Gault)	Starting Lenalidomide Dose
≥ 60 ml/min	15 mg daily on Days 1 - 21 of each 28-day cycle
≥ 30 and < 60 ml/min	5 mg daily on Days 1 - 21 of each 28-day cycle

For patients with normal renal function (creatinine clearance \geq 60 ml/min), the starting dose will be lenalidomide 15 mg daily with escalation to 20 mg if no excess toxicity. For patients with creatinine clearance \geq 30 and $<$ 60 ml/min, the starting dose will be lenalidomide 5 mg daily with escalation to 10 mg if no excess toxicity. The lenalidomide dose may only be increased if the prior treatment cycle was completed without requiring dose modifications, interruptions or delays due to toxicity. Excess toxicity will be defined as grade 3 or 4 non-hematologic toxicity or grade 4 hematologic toxicity (see Section 6.1).

Prophylactic aspirin or low molecular weight heparin are to be given to patients with a high risk of developing DVT/PE or arterial thromboses unless contraindicated. High risk is defined as a history of DVT/PE, a known hypercoagulable state, and/or taking a concomitant medication associated with an increased risk for a thromboembolic event. Patients with diabetes mellitus or coronary artery disease are considered to be at high risk for arterial thromboembolic events.

Prescriptions for lenalidomide must be filled within 7 days. Dosing will be in the morning at approximately the same time each day. Lenalidomide capsules should be swallowed whole, and should not be broken, chewed, or opened. If a dose of lenalidomide is missed, it should be taken as soon as possible on the same day. If it is missed for the entire day, it should not be made up. Patients who take more than the prescribed dose of lenalidomide should be instructed to seek emergency medical care if needed and contact study staff immediately.

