5.5 Duration of Therapy

The study includes an induction phase consisting of 12 cycles of ALR or ALO. Responding subjects will be eligible to enter a maintenance phase. Subjects will continue maintenance ALR or ALO until disease progression, development of unacceptable toxicity, or voluntary withdrawal. Acalabrutinib and lenalidomide can be discontinued after 24 cycles of treatment (12 cycles of induction and 12 cycles of maintenance) for subjects achieving MRD-negative CR during maintenance phase. Subjects have the option to complete study after a total of 3 years of study treatment at the discretion of the treating physician. Subjects can be retreated with acalabrutinib and lenalidomide at time of disease progression.

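### The 15 mg maintenance dose of lenalidomide carries no renal exception, and nothing says whether it or the 5 to 10 mg renal range in Section 5.3.2 governs from cycle 13

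*Combined protocol and SAP*

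**What the plan says.** Maintenance starts at cycle 13: "Responding subjects will be eligible to enter a maintenance phase" (Section 5.1). For both the ALR and the ALO cohort, Section 5.1.2 gives the dose as "Lenalidomide 15 mg on days 1-21". The Study Agent part of the Protocol Summary repeats this line for both cohorts. Neither place mentions renal function.

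Section 3.2 admits patients with CrCl of at least 30 ml/min. Section 5.3.2 then sets the dose by baseline CrCl. At 60 ml/min or above it is 15 mg, escalating to 20 mg. For 30 to <60 ml/min, "the starting dose will be lenalidomide 5 mg daily with escalation to 10 mg if no excess toxicity". The Table 3 entry for that group reads "5 mg daily on Days 1 - 21 of each 28-day cycle", and the table is titled "Lenalidomide Starting Dose Based on Renal Function at Study Entry". A general condition follows: "The lenalidomide dose may only be increased if the prior treatment cycle was completed without requiring dose modifications, interruptions or delays due to toxicity".

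Section 6.3.1 bars re-escalation once lenalidomide has been reduced for toxicity. Section 7.2.3 reports that, in healthy volunteers, roughly two-thirds of a dose leaves the body unchanged in urine.

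**The concern.** The plan recognises that patients with CrCl 30 to <60 ml/min need a lower dose and gives them their own row in Table 3. At cycle 13 the maintenance line states one dose for everyone, and that dose lies above the only range this group has been given. Taken literally, the change also runs the wrong way round: patients with better renal function come down from 20 mg, while those with impaired function go up.

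What is at stake is patient safety in maintenance, with a drug cleared largely by the kidney. Two sites could dose the same kind of patient differently and each cite a section in support. There is also a reporting consequence. The overdose definition in Section 12.2.2 counts any oral amount above the dose that the protocol specifies for that patient. If the specified dose is unclear, 15 mg could be logged as correct at one site and as an overdose at another.

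**Working it through.** The plan gives no per-cycle totals for lenalidomide, so there is no stated figure to reproduce. The check compares the sections and then does simple dose arithmetic.

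**Does any section settle the dose for a patient with baseline CrCl 30 to <60 ml/min at cycle 13?**

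- *Section 5.1.2 and the Summary:* 15 mg, no renal qualifier.
- *Section 5.3.2:* 5 mg, up to 10 mg. It sets no phase limit, and Table 3 refers to each 28-day cycle, which is also the length of a maintenance cycle. Against that, Table 3 is titled as a study-entry starting dose, and maintenance is not mentioned.
- *Condition on increases in 5.3.2:* it asks only whether the prior cycle was free of changes due to toxicity. A patient tolerating 10 mg meets it, so it does not block a move to 15 mg.
- *Sections 6.3.1 and 6.4:* these hold down the dose after a reduction for toxicity. A patient on 5 or 10 mg for renal reasons has had no such reduction. Patients who have been reduced for toxicity are already protected and are not part of this point.
- *Section 5.5:* covers duration only.

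No section gives a renal maintenance dose or an order of precedence.

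**Size of the change if 5.1.2 is followed literally.** Dose per cycle = daily dose × 21 days:

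- 5 mg: 5 × 21 = 105 mg
- 10 mg: 10 × 21 = 210 mg
- 15 mg: 15 × 21 = 315 mg
- 20 mg: 20 × 21 = 420 mg

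Change on entering maintenance:

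| Patient at end of induction | Per cycle before | Per cycle after | Ratio |
|---|---|---|---|
| CrCl 30 to <60, tolerating 10 mg | 210 mg | 315 mg | 315/210 = 1.5 |
| CrCl 30 to <60, still on 5 mg | 105 mg | 315 mg | 315/105 = 3.0 |
| CrCl ≥60, on 20 mg | 420 mg | 315 mg | 315/420 = 0.75 |

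In Table 5, the move from 10 to 15 mg is one level up (Level -1 to Level 0), and the move from 20 to 15 mg is one level down (Level +1 to Level 0). The 3-fold row is a narrow path: it needs a patient who was neither escalated nor reduced over all 12 induction cycles.

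Lenalidomide can first be stopped for MRD-negative CR after 24 cycles, that is, after 12 maintenance cycles. Over 12 uninterrupted cycles the 10 mg patient would receive 12 × 315 = 3,780 mg instead of 12 × 210 = 2,520 mg, a difference of 1,260 mg.

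If the site keeps the renal dose, every one of these increases is zero.

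**The case against.** The strongest reply is that Section 5.1 is an outline of the regimen for patients with normal renal function, with the detail in 5.3. The induction line in 5.1.1 (15 mg, then up to 20 mg) omits the renal exception in the same way, yet a site must already take the renal dose from 5.3.2 for cycles 1 to 12. Such a site has good reason to continue doing so at cycle 13. Table 3 speaks of each cycle, the only escalation given for this group ends at 10 mg, and no sentence expressly authorises 15 mg for it.

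Much of this stands. A reader might argue that 5.1.2 has to override 5.3.2 in order to bring full-dose patients down from 20 mg, and so overrides it for the renal group too. That argument is weak. The CrCl ≥60 row of Table 3 is itself 15 mg in each 28-day cycle, so for those patients 5.1.2 returns to their Table 3 dose and breaks no renal limit.

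A reader might also infer that renal function cannot be known at cycle 13, because CrCl is scheduled at screening only. The documents do not support that either. Chemistry and weight are scheduled on Day 1 of later cycles and Appendix A gives the formula, so CrCl can be recalculated, although the plan neither requires this nor ties a maintenance dose to it. Day 1 laboratory tests and the toxicity rules also continue in maintenance.

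What the reply does not do is close the gap. For induction, 5.3.2 speaks directly to the starting dose and the escalation. For maintenance it is silent, and 5.1.2 states a fixed dose.

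**Conclusion.** The two sections conflict for responders with baseline CrCl 30 to <60 ml/min who have not been reduced for toxicity, and the plan does not resolve the conflict. It is tempting to conclude that the plan prescribes 15 mg to these patients. The text does not show that, because the reading under which 5.3.2 governs is a reasonable one. The finding is that both readings are available and that one of them is unsafe by the plan's own dose limits.

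On the literal reading, the daily dose goes to 1.5 times the top of the group's stated range. The 1,260 mg figure further assumes a patient who reached 10 mg and then had 12 uninterrupted maintenance cycles. The documents do not say how many patients with this CrCl will enrol, respond and reach cycle 13 unreduced, or how any site would read the line, so no expected number can be given. They also give no exposure or toxicity figures for this CrCl range.

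The primary endpoint is read at the end of the 12 induction cycles, so it is unaffected, as is the sample size. The point should be fixed because it bears on dosing safety and the correction is cheap.

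**What to change.** In Section 5.1.2 and in the Protocol Summary, for both cohorts, keep "Lenalidomide 15 mg on days 1-21" and add after it: *for patients dosed for CrCl ≥60 ml/min; patients dosed for CrCl 30 to <60 ml/min stay within the Section 5.3.2 range and do not exceed 10 mg; no dose is raised on entering maintenance after a toxicity reduction (Section 6.3.1).*

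The sponsor should also state the renal maintenance dose itself. Two choices fit the existing text: 5 mg, which parallels the return of full-dose patients to their Table 3 dose, or whichever dose from 5 to 10 mg the patient is tolerating. The documents do not decide between them, and the choice is a clinical one.

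The cost is one clause in four places (two cohorts, two sections). It adds no dose level and no visit, and changes neither the sample size nor the analysis.

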5.2 Schedule of Evaluations

Screening assessments and all scheduled study visits and assessments are outlined in **Table 1 (ALR)** and **Table 2 (ALO)**.

5.2.1 Screening Visit

Study screening begins when the subject signs the written informed consent document (ICD). All screening assessments must be completed within 28 days prior to Registration, with the exception of diagnostic biopsy which has no time limit. All baseline evaluations are to be done within 4 weeks prior to the start of Cycle 1 Day 1 treatment, unless otherwise specified.

- Diagnostic tissue biopsy slides available demonstrating mantle cell lymphoma (**No Time Limit**)
- Bone marrow aspirate and core biopsy (**No Time Limit**)
- Physical examination with history, vital signs including weight, and performance status
- Concomitant medications
- 12-lead Electrocardiogram
- PET scan
- CT scan (or MRI) of neck/chest/abdomen/pelvis (and other areas if indicated to evaluate sites of disease involvement)
- Complete blood count (CBC) with differential
- Serum chemistries to include CMP, LDH, phosphate and uric acid
- Coagulation profile with PT and aPTT
- Creatinine clearance
- Hepatitis B/C, HIV screening

- Thyroid function test (TSH, T4, T3 uptake)
- Pregnancy test (for female of childbearing potential)
- FACT-Lym quality-of-life questionnaires
-

5.2.2 Treatment Phase

5.2.2.1 Cycle 1 Day 1, then Day 1 of all subsequent cycles

- Physical examination with vital signs and performance status
- AE assessment
- Concomitant medications
- CBC with differential
- Serum chemistries to include CMP, LDH, phosphate and uric acid
- Pregnancy test (for females of childbearing potential) (see appendix I)
- Correlative blood samples (Cycles 1, 2, 4, 6, 7, 13, 17, 21, 25, 29, 33 etc)
- Patients who discontinued oral medications and are on rituximab maintenance only, can have study visits on day 1 of cycles when treatment and laboratory studies are required.

5.2.2.2 Cycle 1, Days 8, 15, 22

- Physical examination with vital signs
- AE assessment
- Concomitant medications
- CBC with differential
- Serum chemistries to include CMP, LDH, phosphate and uric acid
- Correlative blood samples
- Subjects on ALO cohort can skip C1D22 visit

5.2.2.3 Cycles 4, 7, 10, 13, 17, 21, 25, then every 6 cycles onward

- Thyroid function test (TSH, T4, T3 uptake)
- HBV viral DNA in HBcAb positive, asymptomatic carrier
- CT scan (or MRI) of neck/chest/abdomen/pelvis (and other areas if indicated to evaluate sites of disease involvement); PET/CT to confirm CR

- Bone marrow aspirate and core biopsy (unilateral) only if otherwise in complete remission – not repeated once negative
- FACT-Lym quality-of-life questionnaires
- Correlative blood samples
- MRD assays at cycles 7 and 13, then every 4 cycles year 2 during maintenance, then every 6 cycles for years 3-5
- Telemedicine/virtual visits will be allowed after cycle 3 of induction during cycles when there is no infusion treatment, where physical exam and vital signs may not be collected.

5.2.3 Treatment Discontinuation

At treatment discontinuation, subjects will undergo off study evaluations within 28 days of last dose.

- Physical examination with vital signs and performance status
- AE assessment
- CBC with differential
- Serum chemistries to include TFT, CMP, LDH, phosphate and uric acid
- Concomitant medications
- HBV viral DNA in HBcAb positive, asymptomatic carrier
- Correlative blood samples
- Pregnancy test (for females of childbearing potential)
- CT scan (or MRI) of neck/chest/abdomen/pelvis (and other areas if indicated to evaluate sites of disease involvement); PET scan at discretion of investigator
- FACT-Lym quality-of-life questionnaires
- Telemedicine/virtual visits will be allowed where physical exam and vital signs may not be collected.
- Follow-up contact every 6 months until death

5.2.4 COVID-19 Pandemic-related Acceptable Protocol Modifications

- Study visits may be impacted due to the COVID-19 pandemic. This may include changes such as phone or virtual visits, visits at alternative locations, or changes in the visit

frequency and timing of study procedures, among others. Every effort should be made to ensure the safety of subjects and site staff, while maintaining the integrity of the study.

- If travel restrictions or other changes in local regulations in light of the COVID-19 pandemic prevent the subject from having blood drawn for laboratory testing at the study site, if possible, arrange for subjects to have laboratory work done at a local lab, hospital, or other facility. Local lab results should be reviewed by the investigator as soon as possible.
- Subject visits may be conducted via phone or video conference. If subjects are unable to be assessed by the study site, vital signs may be collected from another licensed practitioner, or collected by the subject or caregiver as needed. Physical exam (including body weight) may be collected from another licensed practitioner. Concomitant medication and AE assessments visits may be conducted via phone or video conference.
- If a subject is unable to come to the study site to pick up their oral study drug due to COVID-19, a direct-to-patient (DTP) study drug shipment can be made from the study site to the subject if allowed by local regulations.
- Research sample collections may only be collected at the study site and are not to be collected if travel restrictions or other changes in local regulations in light of the COVID-19 pandemic prevent the subject from visiting the study site at a sample collection time point.

